10.2 Planned recruitment rate

Recruitment will take place over 24 months, which will require an overall recruitment rate of 67 per month (which is < 1 participant per centre/month assuming centres can be quickly opened).

The “green” criteria for progression from internal pilot to full trial at 12 months (see below) are entirely realistic based on the recruitment rate in the feasibility trial.

10.3 Statistical analysis plan

A full statistical analysis plan (SAP) will be prepared and approved in advance of the first substantive unblinded analysis of efficacy data.

All analyses will be conducted according to the intention-to-treat principle in accordance with the randomised intervention. A sensitivity analysis will be performed per protocol for the primary outcome, including only those participants who completed the trial in accordance with the approved protocol.

10.3.1 Summary of baseline data and flow of participants

Baseline data will be collected to describe the trial population (so that comparisons can be made with other populations):

- a) Age
- b) Sex – female, male
- c) Primary diagnosis – cancer, non-malignant (with specific diagnosis)
- d) Ethnicity

Baseline characteristics will be summarised by intervention group using appropriate point (e.g. proportions for binary outcomes, means or medians for continuous variables), and interval estimates.

10.3.2 Primary outcome analysis

The primary analysis will use a multilevel regression approach, which recognises the hierarchical nature of the data, and participants nested within centres (clusters). A mixed effects logistic regression will be used to assess the difference in the odds of delirium (defined as a Nu-DESC score ≥ 2 at any point during the trial observation period) between intervention groups, using intervention group as a covariate and adjusting for home country (i.e., England, Wales, Scotland or Northern Ireland) and by type of unit (i.e., hospital or hospice), which were used as stratification variables in the randomisation, disease category (i.e., cancer, non-malignant disease), age (e.g., < 65 years, > 65 years), and sex (i.e., male, female). Centre will be included as a random effect, to allow for correlation in outcomes within clusters. A significance level of 5% will be used to judge significance for the primary outcome measure. The analysis will take into account different “times at risk” by adding an offset term of log (observed days to delirium) to the model, effectively adjusting the binomial denominator to reflect the number of “trials” in each participant.

A sensitivity analysis for the primary outcome will be undertaken per-protocol excluding those participants who did not comply with the protocol. Compliance with the CAH regimen will be defined as receiving $>75\%$ of the prescribed fluids.

10.3.3 Secondary outcome analysis

Secondary outcomes will be handled similarly for dichotomous outcomes, including at the various thresholds for delirium on the NUDESC scale (≥ 1 versus ≥ 2). Survival and time to delirium will be assessed by Kaplan Meier plot and analysed using a Cox regression model. Where there are problems of convergence in models using random effects, centre will be

converted to a fixed effect. Intervention tolerability and adherence to the CAH procedures will be presented. Exploratory analysis (to be detailed in the SAP) will include methods accounting for the repeated observations on outcomes.

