4 TRIAL DESIGN

The trial is a cluster randomised trial (CRT), where the research sites are randomised to one or other intervention. The intervention will become the standard of care at the research site and will be given to all participants unless there is a contraindication to the intervention (or an indication for the alternative intervention).

The CHELsea II trial (definitive trial) leads on from the CHELsea I trial (feasibility trial) [8,9]: the feasibility trial was conducted to ensure that the definitive trial “could be done”. The CHELsea I trial achieved all of the pre-determined criteria for success [9], and so there is no rationale for major amendments to the trial protocol (i.e., trial design, trial methods).

Score	Term	Description
+4	Combative	Overtly combative, violent, and immediate danger to staff
+3	Very agitated	Pulls or removes tube(s) or catheter(s) and aggressive
+2	Agitated	Frequent non purposeful movements
+1	Restless	Anxious or apprehensive but movements not aggressive or vigorous. Frequent movements, nonaggressive, in patient who is not fully alert
0	Alert or calm	
-1	Drowsy	Not fully alert but has sustained (more than 10 seconds) awakening, with eye contact to voice
-2	Light sedation	Briefly (less than 10 seconds) awakens with eye contact to voice
-3	Moderate sedation	Any movement (but not eye contact) to voice
-4	Deep sedation	No response to voice but any movement to physical stimulation
-5	Unarousable	No response to voice or physical stimulation

Table 2 – Modified Richmond Agitation Sedation Scale (m-RASS) [27].

We considered undertaking a “conventional” randomised controlled trial (RCT). However, RCTs are problematic in palliative care, and especially in end-of-life care [29]. Indeed, there have only been three published RCTs of CAH, and these studies recruited very small numbers of participants (i.e., 222 participants in total) [10-12]. Moreover, the principal RCT of CAH failed to meet its target for recruitment [12]. Hence, after reviewing the literature, we decided to undertake a cluster randomised trial [30,31].

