7.3 The randomisation scheme

Randomisation will be undertaken 1:1 by site (cluster), to ensure balance and equal numbers in each intervention group, stratifying by home country (i.e., England, Wales, Scotland or Northern Ireland), and by type of unit (i.e., hospital or hospice). Randomisation will be undertaken by the Trial Statistician at Surrey CTU, using a blocked randomisation with separate blocks (of random length) assigned to hospitals and hospice groups within each of the home countries to ensure balance on these factors.

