8 TRIAL TREATMENTS

The health technology being assessed is clinically-assisted hydration (CAH), i.e., parenteral fluids (intravenous/subcutaneous fluids). Currently, there is no agreed “standard of care”, with some patients receiving CAH during the last days of life, whilst other patients do not receive CAH during the last days of life (but receive oral fluids, and/or regular “mouth care”). Moreover, some patients have CAH withdrawn during the last days of life.

Research sites will be randomised to either “standard intervention A” or “standard intervention B” (see below), and this will become the standard of care at the research site for the duration of this trial. The interventions represent the current typical standards of care in the UK.

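### The fallback of making centre a fixed effect (section 10.3.3) cannot identify the intervention effect, because each centre has only one allocation

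*Protocol*

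**What the plan says.** Four parts of the protocol bear on this point.

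- **Design.** Section 4 describes a cluster trial "where the research sites are randomised to one or other intervention", and section 7.3 randomises sites 1:1. Section 8 adds that "this will become the standard of care at the research site for the duration of this trial". There is no crossover and no stepped introduction.
- **Analysis by allocation.** Section 10.3: "All analyses will be conducted according to the intention-to-treat principle in accordance with the randomised intervention".
- **Planned model.** Section 10.3.2 fits a mixed effects logistic regression "using intervention group as a covariate and adjusting for home country", type of unit, disease category, age and sex. For clustering it says: "Centre will be included as a random effect, to allow for correlation in outcomes within clusters". Section 10.3.3 treats dichotomous secondary outcomes in a similar way.
- **Fallback.** Section 10.3.3: "Where there are problems of convergence in models using random effects, centre will be" "converted to a fixed effect". No other fallback is named, and nothing says that the intervention term is then handled differently.

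**The concern.** A fixed centre effect is a reasonable simplification in an individually randomised multicentre trial, where both arms occur in every centre and the comparison is made within centres. Here there is no within-centre comparison. All information on the intervention lies between centres, and fixed centre effects absorb all between-centre differences.

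For an outcome that reaches the fallback, the analyst would then have either no between-arm estimate or a number without meaning. The dichotomous secondary outcomes include use of delirium medication, audible airway secretions and symptoms, so these are comparisons that readers of the trial will want. A pre-specified fallback should also spare the team from choosing a method after seeing the data, which matters more because section 7.4 makes the trial unblinded. A rule that cannot be followed forces that choice.

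**Working it through.** The plan has no figure of its own to reproduce on this point. The check uses only its layout: 80 centres of 20 participants (section 10.1), 80 × 20 = 1600, split 40/40 by the 1:1 site randomisation.

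**Algebra.** Let D_j be the indicator of centre j and A the indicator of the CAH arm. Since A is constant within each centre, A = Σ D_j over the CAH centres. The linear predictor is α_j + βA. Replace β by β + c, and α_j by α_j − c in every CAH centre. The predictor is unchanged for every participant and every c, so the likelihood is flat in β. This does not depend on sample size, intra-cluster correlation or outcome type.

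**Rank of the design matrix.**

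| Columns | Number of columns | Rank |
|---|---|---|
| 80 centre indicators + arm | 81 | 80 |
| 80 centre indicators + 3 participant covariates (disease category, age, sex) | 83 | 83 |
| the same + arm | 84 | 83 |
| the same + arm + country (3) + type of unit (1) | 88 | 83 |
| No centre term: intercept, arm, country (3), type of unit, 3 covariates | 9 | 9 |

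The residual sum of squares of arm after regression on the centre indicators is 0. Home country and type of unit, which section 10.5 requires in the adjusted analyses, are lost in the same way. The last row shows that it is the fixed centre effects that remove the intervention effect.

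**What a forced fit returns.** Suppose one centre in each arm is omitted, leaving intercept + arm + 78 centre indicators (80 columns, rank 80). The arm coefficient is then the difference in log odds between the two omitted centres. One dataset was simulated with 80 centres of 20, 60% against 50% (true log odds ratio ln(1/1.5) = −0.405) and an intra-cluster correlation of 0.025 placed on the logistic scale. Five choices of omitted pair gave:

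| Pair | Arm coefficient | SE |
|---|---|---|
| 1 | −0.251 | 0.710 |
| 2 | −0.647 | 0.663 |
| 3 | −0.480 | 0.697 |
| 4 | −0.401 | 0.636 |
| 5 | +1.025 | 0.654 |

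The log-likelihood was −1027.889 in all five fits, so goodness of fit cannot tell them apart, and one has the opposite sign. The standard errors are what two sites of 20 would give: √(1/(20 × 0.6 × 0.4) + 1/(20 × 0.5 × 0.5)) = √(0.208 + 0.200) = 0.64. The result rests on 40 participants out of 1600. The 50% reads the 10% reduction as absolute. It affects only this illustration, not the rank result.

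**The case against.** The strongest case on the other side concerns scope and consequence.

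- *The rule is contingent and secondary.* It stands in the secondary outcome section and acts only after a convergence failure. Section 10.3.2 states no such fallback for the primary model. This stands. A reader might infer that the primary result is at risk, since the sentence speaks of random-effects models in general, but the text does not clearly carry it over.
- *Convergence failure may be rare.* This also stands. A reader might infer that failure is likely, but the protocol gives no information on it. Eighty centres of 20 with an intra-cluster correlation of 0.025 and a control rate of 60% is not obviously fragile for delirium-type outcomes.
- *The outcomes reached may be few.* Adverse effects of CAH are the tempting example, being possibly infrequent. However, section 10.3.3 says only that tolerability will be presented, which may be descriptive. Survival and time to delirium are assigned a Cox model with no stated random term, so the rule may not reach them.
- *A suitable constraint rescues the estimate.* With centre nested in arm and centre effects summing to zero, a contrast of average centre effects can be computed. The protocol specifies no such constraint, and the standard error would leave out variation between sites. With the planning values, the variance of a site mean is proportional to 1 + 19 × 0.025 = 1.475, of which 0.975 is within-site. The standard error would be about √(0.975/1.475) = 0.81 of its proper size. This is why the exact wording is not identifiable as specified, rather than beyond any estimation.
- *The team would notice and depart from the rule.* A dropped arm term is visible, and section 10.9 provides for reporting and justifying departures from the SAP. That limits harm but does not make the rule correct. A coefficient printed after another centre has been omitted is easier to miss.
- *This is detail for the SAP.* The SAP was not available. The point, however, is not an omission: the protocol states a method, and the method is wrong for this design.

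**Conclusion.** The concern holds. As written, the fallback in section 10.3.3 cannot identify the CAH effect, for any secondary outcome analysed with a random-effects model that reaches it. The loss is complete: 81 columns, rank 80, and no information left on arm once the centre effects are free. Covariates that vary within centre, and their interactions with arm, would remain estimable, but the main comparison would not.

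This rests on three features that the protocol fixes: sites are the unit of randomisation, one allocation per site holds throughout, and participants are analysed as allocated. Starting or stopping CAH in individual participants (section 7.8) does not change it.

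The finding is a wrong rule of limited reach. It does not show that the primary analysis is compromised or that convergence will fail.

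**What to change.** Delete the clause that converts centre to a fixed effect and replace it with a fallback that keeps the intervention effect estimable and allows for clustering. One workable order is:

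1. Refit with another optimiser or quadrature setting, or collapse sparse covariate levels.
2. If that fails, use GEE, or a model with cluster-robust standard errors, with a small-sample correction in either case.
3. Alternatively, analyse site-level summaries, adjusted for home country and type of unit.

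Other choices that meet the same two conditions would do. It would help to say whether the fallback also covers the primary model, since the present text leaves that open.

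The cost is one sentence in the protocol, with the SAP brought into line if it repeats the rule. No data collection, sample size or patient procedure changes.

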10.4 Subgroup analyses

Subgroup analyses of the primary outcome will be performed for disease category (cancer, non-malignant), age (< 65 years, \geq 65 years), and sex (female, male). Results on these strata will be reported separately and tested by inclusion of the appropriate interaction term in the analysis model.

10.5 Adjusted analysis

Analyses will be adjusted for home country (i.e., England, Wales, Scotland or Northern Ireland) and by type of unit (i.e., hospital or hospice), which were used as stratification variables in the randomisation, disease category (i.e., cancer, non-malignant disease), age (e.g., < 65 years, $>$ 65 years), and sex (i.e., male, female) as described above.

10.6 Interim analysis and criteria for the premature termination of the trial

The statistical analysis will be undertaken at the end of the trial: there will be no planned interim analysis, although this can be requested by the DMEC if felt necessary following periodic review of the data. An internal pilot will confirm continuance of the trial according to satisfaction of recruitment targets.

The CHELsea II trial follows on from the CHELsea I trial (feasibility trial) [8,9]. Nevertheless, the CHELsea II trial will include an internal pilot, which will last for 12 months (from recruitment of the first participant). The criteria for progression from the internal pilot to the full trial are shown in Table 5. Green ("Go") would represent \geq 75% of the initial target recruitment of 800 after 12 months; amber would represent \geq 50% of the initial target recruitment of 800 after 12 months (which would trigger a recovery plan to ensure the overall target recruitment of 1600 after 24 months). Failure to recruit 400 participants, and/or less than 30 sites opened, and/or a recruitment rate $<$ 2 participants/site/month would result in the trial being halted [42].

Progression criteria	Green "Go"	Amber	Red "Stop"
----------------------	------------	-------	------------

		“Action Required”	
Number of sites opened	≥ 40	$\geq 30 (< 40)$	< 30
Recruitment rate / site / month (at end of internal pilot)	≥ 4	$\geq 3 (< 4)$	< 2
Total recruitment (absolute number)	≥ 600	$\geq 400 (< 600)$	< 400
Total target recruitment (% sample size)	$\geq 40\%$	$\geq 25\% (< 40\%)$	$< 25\%$

Table 5 - Criteria for progression (from internal pilot to full trial) at 12 months.

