1 BACKGROUND

The provision of clinically-assisted hydration (CAH) at the end-of-life is one of the most contentious issues in medicine, and indeed within the general population [2]. The reasons for contention include: a) the lack of evidence for/against CAH [3,4]; b) the disparate opinions of healthcare professionals about CAH [4]; and c) the generally positive opinions of patients and their carers about CAH (and the generally negative opinions about withholding/withdrawing CAH) [5,6] It is, therefore, unsurprising that the provision of CAH at the end-of-life is extremely variable within clinical practice (e.g., 12-88% cancer patients in the last week of life) [7].

The CHELsea II trial is a cluster randomised trial of standard end-of-life care with CAH (versus standard end-of-life care without CAH) in patients in the last days of life. The CHELsea II trial (definitive trial) leads on from the Research for Patient Benefit (RfPB) - funded CHELsea I trial (feasibility trial) [8,9], which achieved all of the pre-defined criteria for success, and especially the recruitment criterion (i.e., 200 patients from 12 trial sites in one year) [9]. It should be noted that the feasibility trial only included patients with cancer, but (on the basis of feedback from the HTA Funding Committee) the definitive trial will include patients with cancer and patients with non-malignant disease.

The Cochrane review of medically assisted hydration (aka CAH) for adult palliative care patients concluded that “there are insufficient good-quality studies to make any definitive recommendations. As a result, it is not possible to define the benefits and harms of this treatment clearly” [3]. It identified 6 relevant studies, although only 3 studies were randomised controlled trials (RCTs) [10-12]. However, none of the RCTs addressed the specific issue of the routine use of CAH at the end-of-life.

Thus, Cerchietti et al (2000) included patients with evidence of dehydration (and/or renal failure), and the fluids were only given for 48 hours (and not continued until death) [10]; Bruera et al (2005) only included patients with evidence of dehydration, and the fluids were only continued for 48 hours (and not continued until death) [11]; and Bruera et al (2013) only included patients with evidence of dehydration, and the fluids were continued for a variable duration, i.e., “until the patient was unresponsive, developed progressive coma, or died” [12].

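### The internal-pilot halt line of 2 participants per site per month lies above the protocol's own planned rate of 0.83 when centres open quickly, and the rate has no defined denominator

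*Protocol*

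**What the plan says.** Protocol section 10.1 arrives at 80 centres and 1600 participants. Section 10.2 sets a recruitment period of 24 months and describes the pace needed: "which will require an overall recruitment rate of 67 per month (which is < 1 participant per centre/month assuming centres can be quickly opened". It then says that the green progression criteria "are entirely realistic based on the recruitment rate in the feasibility trial". Section 1 describes the recruitment criterion that the feasibility trial met as "200 patients from 12 trial sites in one year".

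Section 10.6 sets an internal pilot of 12 months with a recruitment target of 800. Its prose halts the trial for fewer than 400 participants, fewer than 30 open sites, or a rate under "2 participants/site/month would result in the trial being halted". The three conditions are joined by and/or. Table 5 repeats the rate criterion in a row labelled "Recruitment rate / site / month (at end of internal pilot"), with green at 4 or more, amber from 3 to below 4, and red below 2. The other rows set green at 40 or more sites, 600 or more participants, and 40% or more of the sample size.

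**The concern.** A halt line should separate a trial that is failing to recruit from one that is on course. Here it stands above the rate that section 10.2 says the trial needs, and it can stop the trial by itself. No interim analysis is planned, so the pilot rule is the only numerical stopping criterion that the protocol fixes. Applied literally, it could end a trial that has met its site and recruitment targets. If it is set aside because it is plainly too strict, a pre-specified rule becomes a matter of discretion.

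**Working it through.** **Inputs.** 1600 participants and 80 centres (10.1); 24 months and 67 per month (10.2); 800 at 12 months and the Table 5 cut-offs (10.6); 200 patients, 12 sites, one year (section 1).

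**1. The planned rate.** 1600/24 = 66.7, which reproduces the 67 per month. 66.7/80 = 0.83 per site per month, which agrees with the stated figure of under 1. The halt line is 2/0.83 = 2.4 times this rate, and the green line is 4/0.83 = 4.8 times.

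**2. That plan at 12 months.** With 80 sites open throughout and 800 recruited:
- sites: 80, green (at least 40);
- total: 800, green (at least 600);
- percentage: 800/1600 = 50%, green (at least 40%);
- rate: 800/(80 × 12) = 0.83, red (below 2).

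At exactly 2 per site per month, 80 sites open for 12 months would recruit 2 × 80 × 12 = 1920, more than the whole trial.

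**3. Dependence on site opening.** If all sites are open throughout, the rate is N/(sites × 12). If sites open linearly over the 12 months (an assumption), on average half are open and the rate per open site-month is N/(sites × 6).

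| Recruited | Sites | Open throughout | Opening linearly |
|---|---|---|---|
| 800 | 80 | 0.83, red | 1.67, red |
| 800 | 40 | 1.67, red | 3.33, amber |
| 600 | 40 | 1.25, red | 2.50, no category |
| 800 | 30 | 2.22, no category | 4.44, green |
| 400 | 30 | 1.11, red | 2.22, no category |

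With sites open throughout, 800 reaches a rate of 2 only if there are no more than 800/(2 × 12) = 33.3, that is 33, sites. With linear opening the limit is 800/(2 × 6) = 66.7, that is 66, sites.

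The denominator matters in the same way. If 40 sites open linearly and recruit 800, the rate is 3.33 per open site-month (amber), but 1.67 (red) if 800 is divided by 40 opened sites and 12 months. The protocol does not say which is meant.

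**4. The feasibility benchmark.** 200/(12 × 12) = 1.39 per site per month if all 12 sites were open all year. A rate of 4 would need only 200/(12 × 4) = 4.2 open months per site on average, and the protocol reports nothing of that kind. For the total rows, 1.39 × 40 × 12 = about 667, which meets both 600 and 640. By contrast, the green rate at the green number of sites over 12 months gives 4 × 40 × 12 = 1920, against a green total of 600.

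**5. Consistency within Table 5.** Rates from 2 to below 3 have no category. The green total is 75% of 800 = 600, which is 600/1600 = 37.5%; the percentage row asks for 40% of 1600 = 640. A total of 600 to 639 is therefore green on one row and amber on the next. The red cuts agree: 25% of 1600 = 400.

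**The case against.** The best defence is that the figure of under 1 per centre is conditional on quick opening, while Table 5 treats 40 of 80 sites at 12 months as green. Staggered opening is therefore foreseen. The rate row also refers to the end of the pilot, when monthly accrual may be well above 67: with 40 sites opening linearly and 800 recruited, month-12 accrual would be about 3.33 × 40 = 133. This stands as far as it goes. A reader might infer that any trial recruiting to target must be halted; the documents do not support that, because 40 gradually opened sites clear the line. It does not rescue the rule, since the outcome then turns on an opening pattern and a denominator that the protocol leaves open. Even 80 sites opening linearly stay red.

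A reader might also infer that the feasibility trial recruited at a red rate and that the claim of realism is false altogether. That goes too far. The 1.39 is an average implied by the criterion that was met, not a reported rate per open site, and it is compatible with the green recruitment totals.

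Finally, the 600 versus 640 mismatch never triggers a halt, and none of this biases the treatment effect or the type I error.

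**Conclusion.** The halt criterion is wrong as written. Under the section 10.2 plan with centres opened quickly, a trial that is green on the other three rows is red on rate, at 0.83 against 2, and that alone stops it. The conflict also appears at 800 recruited with 34 or more sites open throughout, and with 80 sites opening linearly over 12 months (1.67). It does not appear when fewer sites open gradually: 40 opening linearly give 3.33 for 800 and 2.5 for 600, although the latter has no category. These results assume constant recruitment per open site and, where stated, linear opening.

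The statement that the green criteria are realistic is unsupported for the rate row only. The gap from 2 to below 3 is a real defect whatever the assumptions. The 40% entry is a minor one.

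**What to change.** Remove the per-site rate from the halt sentence in section 10.6 and from Table 5, because the sites-opened and total-recruitment rows already govern progression. If the rate is kept, derive contiguous green, amber and red bands that agree with those two rows and with the 67 per month plan, and state the denominator, for example open site-months. The planned rate of 0.83 should not sit on a band boundary.

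Set the green percentage to at least 37.5%, to match 600 (75% of 800). Limit the sentence on realism in section 10.2 to the rows that the feasibility figures support.

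The cost is one table and two sentences, with the agreement of the steering committee and the funder. Nothing changes for participants.

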10 STATISTICS AND DATA ANALYSIS

10.1 Sample size calculation

The sample size is based on a “clinically meaningful” reduction in the proportion of participants developing delirium in the CAH intervention group (versus the non-CAH intervention group): a figure of 10% was deemed to be appropriate by the clinicians involved in the trial, and this figure was supported by clinical colleagues (i.e., palliative care doctors / nurses), and members of the local PPI group.

To demonstrate a reduction of 10% in the proportion of participants developing delirium (defined as having a score of > 0 on the Nu-DESC scale) would require 1038 evaluable participants with 90% power and at a significance level of 0.5. The calculation assumes the incidence of delirium in the non-CAH intervention group of 60% (as observed in the feasibility trial). To account for clustering in the responses of participants within centres of size 20, the sample size will be inflated by 1.475 using an estimate of the intra-cluster correlation of 0.025 (as observed in the feasibility trial). A further allowance of 5% for attrition suggests that 80 centres will be required (delivering 1600 participants).

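### The halt limit of 2 participants per site per month is 2.4 times the 0.83 that section 10.2 plans, so a trial on plan with quickly opened sites falls in Red

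*Protocol*

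**What the plan says.** - **Protocol 10.1** concludes that "80 centres will be required (delivering 1600 participants", based on 20 participants per centre.
- **Protocol 10.2** states: "Recruitment will take place over 24 months, which will require an overall recruitment rate of 67 per month". It puts this at fewer than one "participant per centre/month assuming centres can be quickly opened". It then says that the Green progression criteria "are entirely realistic based on the recruitment rate in the feasibility trial".
- **Protocol 1 (Background)** gives the feasibility trial's recruitment criterion, which was met, as "200 patients from 12 trial sites in one year".
- **Protocol 10.6** sets a 12-month internal pilot with a recruitment target of 800. The trial stops for fewer than 400 participants, fewer than 30 sites opened, or a rate below "2 participants/site/month would result in the trial being halted". The three conditions are joined by and/or.
- **Table 5** has a row labelled "Recruitment rate / site / month (at end of internal pilot"), with Green at 4 or more, Amber at 3 to below 4 and Red below 2. Its other rows put Green at 40 or more sites and 600 or more participants, and Red at fewer than 30 sites and fewer than 400 participants.

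**The concern.** A progression rule should separate a trial that is failing to recruit from one that is keeping to its plan. Here the planned pace per site is less than half the limit at which the same protocol halts the trial. The other two stop conditions need not be met for that to happen.

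Applied as written, the rule could end a trial that is recruiting as intended. If the row is set aside because it is plainly out of line, the decision at 12 months becomes ad hoc, which pre-specified criteria are meant to prevent. The row also leaves a range of rates with no outcome, and section 10.2 defends it with feasibility data that do not reach its Green limit.

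**Working it through.** **Inputs.** 1600 participants, 80 centres, 20 per centre (10.1). 24 months, 67 per month (10.2). Rate limits 2, 3 and 4; 800 target at 12 months; Green minimum of 40 sites and 600 participants (10.6 and Table 5). Feasibility trial: 200 patients, 12 sites, one year (Background).

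**1. Reproduce the planned rate.** 1600 / 24 = 66.7 per month, matching the stated 67. 66.7 / 80 = 0.83 per site per month, matching the stated figure of below 1. The cluster size gives the same answer: 20 / 24 = 0.83.

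**2. Compare with the limits.** Red: 2 / 0.83 = 2.4 times the plan. Green: 4 / 0.83 = 4.8 times the plan. A rate of 2 held for 24 months would be 48 participants per site, against the 20 assumed.

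**3. Flat 67 per month, by number of open sites.**

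| Open sites | Rate per site per month | Table 5 |
|---|---|---|
| 33 | 67 / 33 = 2.03 | no category |
| 34 | 67 / 34 = 1.97 | Red |
| 40 | 67 / 40 = 1.68 | Red |
| 60 | 67 / 60 = 1.12 | Red |
| 80 | 67 / 80 = 0.84 | Red |

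**4. Sensitivity to site opening, with the 800 target met at 12 months.** The protocol does not say whether the denominator is sites or open site-months. Linear opening over 12 months is an assumption; it gives sites x 6 open site-months.

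| Sites at month 12 | All open throughout: 800 / (sites x 12) | Linear opening: 800 / (sites x 6) |
|---|---|---|
| 40 | 1.67 (Red) | 3.33 (Amber) |
| 60 | 1.11 (Red) | 2.22 (no category) |
| 80 | 0.83 (Red) | 1.67 (Red) |

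Under linear opening the rate falls below 2 once 800 / (6 x 2) = 66.7 sites is exceeded.

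**5. Green on rate against the other rows.** With 40 sites open throughout: 4 x 40 x 12 = 1920 participants, more than the whole trial. With linear opening: 4 x 40 x 6 = 960. Both exceed the 800 target and the 600 that is Green on total.

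**6. Feasibility rate.** All 12 sites open all year: 200 / (12 x 12) = 1.39. Open half the year on average (an assumption): 200 / (12 x 6) = 2.8. Both are below 4.

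**7. Gap.** Amber starts at 3 and Red ends below 2, so 2 to below 3 has no outcome. This needs no assumption.

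**The case against.** The strongest reply is that 0.83 spreads recruitment over 80 sites open from the first day, whereas Table 5 treats 40 opened sites at month 12 as Green and so allows for gradual opening. Per open site-month, a trial that meets its 800 target can then exceed 2 (step 4). This stands, and it limits what can be claimed. Three stronger readings are tempting, and the document does not support them:

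- *Any trial on target would be halted.* This holds under section 10.2's premise of quick opening, or at a flat 67 per month with 34 or more sites. It does not hold under every opening pattern.
- *A trial that is Green on sites and on total is necessarily Red on rate.* 600 / (40 x 12) = 1.25 is Red only if all 40 sites are open all year. With linear opening, 600 / (40 x 6) = 2.5, which has no category.
- *The feasibility trial would itself have been Red.* The figure of 1.39 assumes that all 12 sites were open all year, and the protocol does not give open site-months. What can be said is that it falls short of Green on either assumption in step 6.

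The row label might also mean the rate in the last pilot month. After 600 recruits, finishing on time needs (1600 - 600) / 12 = 83.3 per month. That is 1.04 per site with 80 sites (Red) and 2.08 with 40 (no category). This reading does not always give Red, but it does not make the row workable.

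Nor does staggered opening rescue the limits. If each open site recruits at a constant rate, the linear scenarios in step 4 end the pilot at about 133 participants per month (3.33 x 40), twice the planned 67, and still none reaches Green. Finally, the realism claim in section 10.2 covers the Green criteria as a group. The site and total rows (1.25 per site per month) sit comfortably with 1.39; only the rate row does not.

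**Conclusion.** The point holds in qualified form. The rate limits in section 10.6 and Table 5 conflict with section 10.2, and nothing else in the protocol resolves the conflict. The halt limit is 2.4 times the planned rate and Green is 4.8 times. Under section 10.2's own assumption of quickly opened centres, a trial exactly on plan meets a stop criterion that can act alone. Whether it would do so under slower opening cannot be settled, because the row defines neither its denominator nor its time window; that omission is part of the defect.

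Two parts do not depend on the opening pattern: the unclassified range from 2 to below 3, and the 0.83 that follows from the protocol's planning figures. That Green is out of reach for a trial meeting its 800 target from 40 sites holds under both opening patterns examined. The realism claim is unsupported for the rate row under both feasibility assumptions. The defect concerns the decision to continue the trial, not the estimand or the analysis.

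**What to change.** **Preferred.** Delete the recruitment-rate row from Table 5 and the matching halt clause in section 10.6. The site and total rows already define the pace that is needed.

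**Alternative.** Keep the row, but:

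1. define the denominator (for example, open site-months) and the time window;
2. derive contiguous bands from the planned site-opening schedule;
3. check that the bands agree with section 10.2 and with the site and total rows.

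Do not simply apply the 75% and 50% fractions from section 10.6 to 0.83. That gives 0.63 and 0.42, which presuppose 80 sites open from day one. At 40 sites, 0.63 x 40 x 12 = 302 participants, which would be Green on rate and Red on total.

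**In either case.** Correct the sentence in section 10.2 so that it no longer claims feasibility support for a Green rate of 4.

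The cost is a protocol wording amendment, with no extra participants or data. It should be made before the 12-month progression decision.
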